9. REGULATORY AND REPORTING REQUIREMENTS

Contact details for personnel connected with this study are provided on the title page at the front of this protocol. Patient registration procedures are described in Section 4.

9.1 Regulatory Responsibilities

9.1.1 Protocol chair

The protocol chair (=PI), (Name) is responsible for the following tasks:

- Coordinating, developing, writing, submitting, and obtaining IRB-approval for the protocol as well as its subsequent amendments.
- Assuring that all study personnel are using the correct version of the protocol.
- Taking responsibility for the overall conduct of the study and for monitoring the progress of the study.
- Reviewing and ensuring reporting of serious adverse events (SAEs).
- Reviewing data from all patients.

9.1.2 Study Coordinator

The study coordinator, (Name), is responsible for the following tasks:

- Ensuring that IRB approval has been obtained prior to patient registration, and maintaining copies of IRB approvals (including approval of amendments).
- Managing patient registration.
- Collecting and compiling data from each patient.
- Establishing procedures for documentation, reporting, and submission of AEs/ SAEs to the protocol chair (Name) and other applicable parties.
- Facilitating audits by securing selected source documents and research records from participating patients for audit.

9.1.3 Study personnel

Study personnel (co-investigators, research nurses) are responsible for these tasks:

- Following the protocol as written, and Good Clinical Practice (GCP) guidelines.
- Submitting data to the project manager.
- Registering all patients by submitting the patient registration form and signed informed consent form promptly.
- Providing sufficient experienced clinical and administrative staff and adequate facilities and equipment to conduct the trial according to the protocol.
- Maintaining regulatory binders and providing copies of all required documents to the project manager.
- Collecting/submitting data according to the schedule specified by the protocol.

9.2 Data Management

Data collected during this study will be entered into a secure database. The study coordinator will be responsible for the initial study configuration and setup of the database and for any future changes.

9.2.1 Case report forms

Case report forms (CRFs) will be generated by the study coordinator for the collection of all study-related data. Investigators and study personnel will be responsible for ensuring that the CRFs are kept up-to-date.

9.2.2 Source documents

Investigators and study personnel will record clinical data in each patient's source documents (*i.e.*, the patient's medical record). Source documentation will be made available to support the patient research record. Study monitors will review entries on the CRFs at regular intervals, comparing the content with the source documents.

9.2.3 Record retention

The investigator will maintain adequate and accurate records to enable the conduct of the study to be fully documented and the study data to be subsequently verified. After study closure, the investigator should maintain all source documents, study-related documents, and the CRFs. Because the length of time required for retaining records depends upon a number of regulatory and legal factors, documents should be stored until the investigator is notified that the documents may be destroyed. In this study, records are to be retained and securely stored for a minimum of 3 years after the completion of all study-related activities.

9.3 Study Monitoring and Quality Assurance

Data and safety monitoring will follow Level Medium under the SKCCC Data and Safety Monitoring Plan. *The SKCCC Compliance Monitoring Program will provide external monitoring for JHU-affiliated sites in accordance with SKCCC DSMP (Version 6.0, 02/21/2019). The SMC Subcommittee will determine the level of patient safety risk and level/frequency of monitoring.* Additionally, scheduled meetings will take place monthly and will include the protocol principal investigator, research nurse, data manager, and, when appropriate, the collaborators, sub-investigators, and biostatistician involved with the conduct of the protocol.

During these meetings the investigators will discuss matters related to: safety of protocol participants, validity and integrity of the data, enrollment rate relative to expectation, characteristics of participants, retention of participants, adherence to protocol (potential or real protocol violations), data completeness, and progress of data for secondary objectives.

10. STATISTICAL CONSIDERATIONS

10.1 Study Design, Sample Size, and Study Endpoints

For the primary outcome: pre- and post-treatment M2-TAM infiltration will be compared using a paired t-test, or nonparametric signed rank test if data don't conform to a Gaussian distribution. Power is based on the paired t-test. With 20 patients, we have the power (\geq 81%) to detect a decrease of \geq 0.67 standard deviation unit (effect size = 0.67) (14). This is likely to be conservative as we observed a much larger difference in M2-TAM levels between primary and

metastatic tumors in our data. Power calculated using PASS v. 11 (NCSS Software, Kaysville, UT).

For the secondary analysis of safety, we will use a continuous toxicity monitoring approach with sequential dose-limiting toxicity boundaries (13). Patients will be evaluated for AEs after neoadjuvant dupilumab. We consider a 15% rate of Grade \geq 3 AEs to be unacceptable and indication to halt the trial. Accrual will continue until the number of Grade \geq 3 AEs equals or exceeds the boundary for a given number of patients, or the completion of 20 patients without crossing any toxicity boundaries. The table below shows the schedule of accrual and associated toxicity boundaries.

Number of patients:3	4	5	6	7	8	9	10	11	12	13	14	15	16	17	18	19	20
Toxicity Boundary: 3	3	4	4	4	4	5	5	5	6	6	6	6	7	7	7	7	7

The AE rate and 95% confidence interval will be calculated, either at trial halt or completion of accrual.

Secondary analyses of other immune infiltrate cells will be compared using a paired t-test, or nonparametric signed rank test if data don't conform to a Gaussian distribution. Other secondary analyses will include calculating the rate and 95% confidence interval (CI) for complete response rates, and undetectable post-treatment PSA, and paired t-tests for the secondary outcome biomarkers listed above. In exploratory analyses we will evaluate whether # of biopsy cores evaluated, patient, or clinical factors correlate with extent of decrease in infiltration, although the small sample size limits these analyses purely to hypothesis generating.

Power. For the primary outcome of pre- vs. post-treatment decrease in M2-TAM infiltration, power is based on the paired t-test. With 20 patients, we have the power (\geq 81%) to detect a decrease of \geq 0.67 standard deviation unit (effect size = 0.67) (14). This is likely to be conservative as we observed a much larger difference in M2-TAM levels between primary and metastatic tumors in our data. Power calculated using PASS v. 11 (NCSS Software, Kaysville, UT). The continuous toxicity monitoring design with n=20 above has probability = 0.048 of early stopping if the Grade \geq 3 AE rate is <15%. Toxicity boundaries calculated using software developed by Ivanova (13)

(http://cancer.unc.edu/biostatistics/program/ivanova/ContinuosMonitoringForToxicity.aspx)

Frequency, types, and grades of adverse events in each treatment group will be measured using the NCI Common Toxicity Criteria version 4.0, and will be summarized using descriptive statistics. Formal safety assessments will be performed from the time of first administration Dupilumab until the 60th postoperative day.

10.1.2: **Early stopping rule for feasibility:** We do not anticipate an increase in the surgical difficulty with the use of neoadjuvant DUPILUMAB. Men who have had acute (post-biopsy) and prolonged issues (chronic prostatitis) with prostate infection/inflammation are fairly routine in urologic surgical practice, and we anticipate that the immune infiltrate potentially induced by DUPILUMAB would not pose a substantial increase in surgical difficulties. However, in addition to safety, feasibility will be monitored separately. The feasibility rule for this study will be based on a change in surgical outcomes beyond what may be expected for patients without presurgical interventions and that may be attributable to the study drug. These events would include: (1) average blood loss in excess of 2500 mL, (2) average operative time in excess of 3.5 hours, and (3) average hospital stay in excess of 4 days. These values are

approximately 2 standard deviations above the average surgical outcomes for men undergoing radical prostatectomy at Johns Hopkins Hospital.

We require that the probability that the surgery will not be complicated by these events to be high (≥90%). We will monitor this endpoint after every patient. If it becomes apparent that the surgeries are being negatively impacted by the pre-surgical investigational treatments, then the study will be suspended for review. This stopping rule will halt enrollment if the posterior probability of no complications <0.90 is greater than 80%. The prior probability for this rule has a Beta-distribution with parameters of 9 and 1, based on the expectation that these treatments will not impact the feasibility of surgery. Instances where the study would be temporarily suspended are listed below.

Stopping rules:

- Not feasible if both of the first 2 patients have surgical complications.
- Not feasible if two of the first 3 patients have complications.
- Not feasible if 2 out of the first 4 patients have complications.
- Not feasible if 3 out of the first 6 patients have complications.
- Not feasible if 4 out of the first 8 patients have complications.
- Not feasible if 5 out of the first 10 patients have complications.
- Not feasible if 6 out of the first 12 patients have complications.
- Not feasible if 7 out of the first 14 patients have complications.
- Not feasible if 8 out of 16 patients have complications.

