10.5.2 Sample size calculation

For the primary outcome: pre- and post-treatment M2-TAM infiltration will be compared using a paired t-test, or nonparametric signed rank test if data don't conform to a Gaussian distribution. Power is based on the paired t-test. With 20 patients, we have the power (\geq 81%) to detect a decrease of \geq 0.67 standard deviation unit (effect size = 0.67) (14). This is likely to be conservative as we observed a much larger difference in M2-TAM levels between primary and metastatic tumors in our data. Power calculated using PASS v. 11 (NCSS Software, Kaysville, UT).

For the safety analysis, we will use a continuous toxicity monitoring approach with sequential dose-limiting toxicity boundaries (14). Patients will be evaluated for AEs after neoadjuvant dupilumab. We consider a 15% rate of Grade >3 AEs to be unacceptable and indication to halt the trial. Accrual will continue until the number of Grade >3 AEs equals or exceeds the boundary for a given number of patients, or the completion of 20 patients without crossing any toxicity

boundaries. The table below shows the schedule of accrual and associated toxicity boundaries.

Number of patients:3 17 18 19 20	4	5	6	7	8	9	10	11	12	13	14	15	16
Toxicity Boundary: 3 7 7 7 7 7	3	4	4	4	4	5	5	5	6	6	6	6	7

The AE rate and 95% confidence interval will be calculated, either at trial halt or completion of accrual.

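### The toxicity boundary stops the trial only about 5% of the time at the 15% Grade ≥3 rate that the plan calls unacceptable

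*Combined protocol and SAP*

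**What the plan says.** Section 10.1 sets the safety criterion: "We consider a 15% rate of Grade \geq 3 AEs to be unacceptable and indication to halt the trial". The operating rule follows: "Accrual will continue until the number of Grade \geq 3 AEs equals or exceeds the boundary for a given number of patients", or until "the completion of 20 patients without crossing any toxicity boundaries". The boundary table starts at patient 3 and ends at patient 20. The synopsis repeats all of this.

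The power paragraph of 10.1, also repeated in the synopsis, gives one operating characteristic: "The continuous toxicity monitoring design with n=20 above has probability = 0.048 of early stopping if the Grade \geq 3 AE rate is <15"%. It attributes the boundary to published continuous-monitoring software: "Toxicity boundaries calculated using software developed by Ivanova (13").

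Section 10.5.2 restates the criterion, again calling a 15% rate of such "AEs to be unacceptable and indication to halt the trial". There the threshold is printed as Grade >3 instead of Grade ≥3, and the method is credited to reference 14 instead of reference 13. The Grade >3 may be an artefact of text extraction, but it should be checked.

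No section gives a stopping probability at any rate of 15% or higher.

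**The concern.** A rate that is an indication to halt should be one at which the rule is likely to halt. A stopping probability near 0.05 is what a designer aims for at the rate considered acceptable, where stopping would be a mistake. The plan gives 15% both roles: the criterion sentence makes it the rate to guard against, and the power paragraph makes it the reference for false stopping.

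An IRB or monitoring committee reading the criterion sentence would believe the trial is protected against a 15% rate of severe events. This is the only numerical rule for drug toxicity in the plan; the rule in 10.1.2 concerns surgical feasibility.

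There is a second, smaller problem. The rule counts adverse events but the boundary is indexed by patients. If one man has two Grade ≥3 events, the text does not say whether he adds one or two to the count. Two people applying the rule to the same data could reach different decisions.

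**Working it through.** **Inputs, all from section 10.1.** Maximum of 20 patients; stop when the cumulative count is at or above the boundary; one look after each patient from the third onward.

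| Patients | 3–4 | 5–8 | 9–11 | 12–15 | 16–20 |
|---|---|---|---|---|---|
| Boundary | 3 | 4 | 5 | 6 | 7 |

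**Method.** Let each patient independently have a Grade ≥3 event with probability p, counted at most once. Let f(n, k) be the probability of having k affected patients after n without having stopped. Then

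f(n, k) = (1 − p)·f(n−1, k) + p·f(n−1, k−1),

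and at each look the mass with k at or above the boundary is removed and added to the stopping probability.

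**Reproducing the plan's figure (p = 0.15).**

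- Patient 3: 0.15³ = 0.0034.
- Patient 4: two affected among the first three, then a third: 3 × 0.15² × 0.85 × 0.15 = 0.0086. Running total 0.0120.
- Through patient 8: 0.0273.
- Through patient 15: 0.0392.
- Through patient 19: 0.0442.
- Through patient 20: 0.0480.

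The total of 0.0480 matches the stated 0.048. A simulation of 1,000,000 trials gave 0.0482. The plan's figure is therefore the value at a rate of exactly 15%, with each patient counted once and the look at patient 20 included.

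**The same recursion at other true rates.**

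| True Grade ≥3 rate | Probability of stopping |
|---|---|
| 5% | 0.001 |
| 10% | 0.010 |
| 14% | 0.037 |
| 15% | 0.048 |
| 20% | 0.136 |
| 25% | 0.281 |
| 30% | 0.461 |
| 35% | 0.641 |
| 40% | 0.790 |
| 50% | 0.953 |

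At 15% the trial completes without crossing with probability 1 − 0.048 = 0.952, and expected enrolment is 19.5 of 20. Stopping becomes more likely than not only at a true rate of about 31%, and reaches 80% at about 40%. The lowest observed proportion that crosses anywhere in the table is 7/20 = 35%. A final count of 6/20 = 30%, twice the rate called unacceptable, does not cross at patient 20.

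**Counting events instead of patients.** The documents give no figure for events per affected patient, so this step is an assumption: each affected patient has 1 + Poisson(m − 1) Grade ≥3 events, with mean m. At a 15% patient rate the same recursion gives:

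| Mean events per affected patient | Probability of stopping |
|---|---|
| 1 | 0.048 |
| 1.1 | 0.10 |
| 1.25 | 0.19 |
| 1.5 | 0.32 |
| 2 | 0.52 |

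**The case against.** **The table and its stated probability agree.** Read as a rule that stops only on evidence that the rate exceeds 15%, the boundary is correctly computed, and 0.048 is a valid upper limit for every rate below 15%. On this reading the fault is one badly worded sentence. The arithmetic stands, and this may well be what was intended. But the plan says that 15% is itself an indication to halt, and even at 20% the rule stops only 14% of the time. The reader is told neither.

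**The counting unit can be inferred.** A rate compared with a boundary indexed by patients is naturally read per patient, and the reproduced 0.048 supports that. Sections 8.3.1 and 10.4.1 count repeat occurrences once per patient, and 6.4.3.2 generally discontinues therapy after a related Grade ≥3 event, which would limit repeats. This makes the per-patient reading likely but does not settle it. Sections 8.3.1 and 10.4.1 govern summaries, and under 8.3.1 two different events in one man still count separately. The higher figures, such as 0.32 and 0.52, depend on assumed means. Counting events also makes stopping more likely, so this point does not add to the under-protection at 15%. It shows only that the rule is ambiguous.

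**Other safeguards exist.** There are monthly team meetings and external monitoring (9.3), SAE reporting to the monitoring committee and IRB (7.5.2), and authority for the principal investigator or medical monitor to close accrual (11.5). These matter, but none has a numerical toxicity threshold and none reconciles the two statements.

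**Safety is a secondary analysis.** The primary test does not depend on the boundary. That is true, but a halting criterion has to mean what it says whatever the rank of the endpoint.

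**Conclusion.** The concern holds. The criterion sentence and the boundary contradict each other: at the 15% rate called unacceptable, the trial stops with probability 0.048 and runs to 20 patients with probability 0.952. The 0.048 belongs to a rate of exactly 15% and is only an upper limit below it (0.010 at 10%). The stopping probabilities that would show how much protection the rule gives are missing from the plan.

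These figures assume one yes/no outcome per patient, independence between patients, and each outcome known before the next look. The last is optimistic, because formal safety assessment runs to the 60th postoperative day. The event-versus-patient ambiguity is real but secondary, and its size depends on an assumption the documents cannot supply.

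**What to change.** Reconcile the criterion sentence with the boundary in the synopsis, 10.1 and 10.5.2, by one of two routes.

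- **(a) Keep the boundary.** Describe 15% as the highest acceptable rate, remove the statement that it is unacceptable and a reason to halt, give 0.048 as the stopping probability at a rate of exactly 15%, and print the stopping probabilities from 20% to 50%. Cost: wording and one small table.
- **(b) Keep 15% as the unacceptable rate.** Recompute the boundary from a lower acceptable rate chosen by the sponsor, and state the stopping probability at 15%. Cost: one re-run of the boundary software and acceptance of a higher chance of early stopping.

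Under either route, define the count as patients with at least one qualifying event in all three places. Also reconcile 10.5.2 with 10.1 on the grade threshold (>3 against ≥3) and on the cited reference (14 against 13). Neither route needs more patients.

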Target population	Inclusion criteria • Histologically confirmed prostate adenocarcinoma • Clinical stage T1c-T3b, N0, M0 • Gleason sum 7-10 • At least 2 positive cores at biopsy • Prior decision to undergo radical prostatectomy • Adult male ≥18 years of age • ECOG performance status 0-1, or Karnofsky score ≥ 70% • Adequate kidney, liver, and bone marrow function • Willingness to sign informed consent and adhere to study requirements Exclusion criteria: • Presence of known lymph node involvement or distant metastases • Prior radiation, hormones, biologics, or chemotherapy for prostate cancer • Prior immunotherapy/vaccine therapy for prostate cancer • Concomitant treatment with hormonal therapy or 5□-reductase inhibitors • Use of experimental agents for prostate cancer within the past 3 months • History of autoimmune disease requiring systemic immunosuppression • History of other lethal malignancy within 3 years • Uncontrolled major infectious, cardiovascular, pulmonary, hematologic, or psychiatric illnesses that would make the patient a poor study candidate			

- illnesses that would make the patient a poor study candidate
- significant eye disease

Start date/ Initial patients are expected to be entered in July 2018. With an estimated enrollment rate of 2-3 patients per month, accrual is expected to last 8-10 months.

Sample 20 evaluable patients (*i.e.* those that undergo prostatectomy)

size

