4.2 Expected Enrollment

A total of 20 patients will be included in this study. The first patients are expected to be enrolled in August 2018, once the protocol has been approved by the IRB. With an estimated enrollment rate of 2-3 patients per month, accrual is expected to be completed in 10 months.

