5. STUDY PLAN

5.1 Overview and Schema

This is a single-center, single arm, open-label phase II study evaluating the safety, antitumor effect, and immunogenicity of neoadjuvant DUPILUMAB given prior to radical prostatectomy in men with high-risk localized prostate cancer. Patients will be recruited from the outpatient Urology clinic. Men will be treated with dupilumab 600 mg s.q. on day 1, and then 300 mg s.q. on days 8, 15, 22, 29, 36, 43. They will then undergo surgery on day 57. 14 days after the last dose of Dupilumab, prostate glands will be harvested at the time of radical prostatectomy, and prostate tissue will be examined for the secondary endpoints. Follow-up evaluation for adverse events will occur 30 days and 60 days after surgery. Patients will then be followed by their urologists according to standard institutional practices, but will require PSA evaluations every 3 (\pm 1) months during year 1 and every 6 (\pm 2) months during years 2-3.

Table 1STUDY CALENDAR

Every effort should be made to keep visits, tests, and procedures on schedule. Acceptable deviations are listed below.

	Screening Evaluationª	Treatment Days (1, 8,15, 22, 29, 36, 43) (+/- 1 day)	Radical Prostatectomy Day 57 (+/- 3 days)	Follow-up, 30, and 60 Days Post-op (+/- 1 wk) ^{h,i}	LTFU (+/- 1 Month) ⁱ
Informed consent	Х				
Medical history	Х				
Review of medications	Х	Х	х	х	
Physical examination	Х	Х			
Vital signs	Х	Х	х		
Height and weight	Х	Х	х		
Performance status	Х	Х	х	х	
CT and bone scan ^b	(X)				
Hematology labs, coagulations ^c	х	х	Х	х	
Chemistry labs ^d	Х	Х	х	Х	
Serum PSA ^e	Х		х	Х	Х
DUPILUMAB dose		Х			
Toxicity assessment	X			X	
Surgical specimen ^f			Х		
Pathologic review ^g	Х		Х		

a: The screening (pre-treatment) evaluation should be conducted within 42 days (±4 days) of starting protocol therapy.

b: Staging CT (if allergic to CT scan contrast, obtain MRI with contrast) and bone scans should only be performed if clinically indicated, and are not mandatory.

c: Hematology laboratories include hemoglobin, hematocrit, white blood cell count with differential (including absolute eosinophil count), and platelets. In addition, prothrombin time (PT/INR) and activated partial thromboplastin time (APTT) should be checked at screening, then as clinically indicated.

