5.4 Radical Prostatectomy

The following must be performed on the day of radical prostatectomy, which itself should occur 56 (± 3) days after the administration of first dose of DUPILUMAB.

- medical history
- performance status
- physical examination, including vital signs
- review of medication list
- review of toxicity/adverse events
- hematological laboratories and serum chemistry profile
- serum PSA
- collection of prostatectomy tissue for analysis of study endpoints
- pathological processing of prostatectomy specimen according to standard procedures

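### The Grade ≥3 AE rate and its 95% CI are timed at trial halt or completion of accrual, which does not fit the plan's own safety window to postoperative day 60

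*Combined protocol and SAP*

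**What the plan says.** Section 10.1 monitors Grade ≥3 AEs against a boundary table. Accrual continues until a boundary is reached "or the completion of 20 patients without crossing any toxicity boundaries". It then says: "The AE rate and 95% confidence interval will be calculated, either at trial halt or completion of accrual". The same sentence stands in the statistical part of the synopsis and in section 10.5.2.

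Later in section 10.1, and in the safety entry of the synopsis: "Formal safety assessments will be performed from the time of first administration Dupilumab until the 60th postoperative day". Section 5.4 places surgery 56 (±3) "days after the administration of first dose of DUPILUMAB", and section 5.1 agrees: "They will then undergo surgery on day 57".

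On enrolment, section 4.2 says "A total of 20 patients will be included in this study" and "With an estimated enrollment rate of 2-3 patients per month, accrual is expected to be completed in 10 months". The synopsis gives 8-10 months and describes the sample as "20 evaluable patients", explained there as men who undergo prostatectomy.

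Sections 5.6, 8.3.1 and 10.3.2 put every man with at least one dose in the safety analysis. No section gives a data cutoff for the AE rate or requires the last man to reach day 60 first.

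**The concern.** This point concerns the final safety estimate, not the monitoring boundary. The timing sentence is the only one in the plan that says when this rate and interval are computed. If the analyst follows it when the 20th man enters, that man has almost no follow-up and several men before him have not been operated on. All would count fully in the denominator, while some of their events would not yet have happened.

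Two things are at stake. The plan treats a 15% rate of Grade ≥3 AEs as unacceptable, so a shortfall of a few points can move the estimate across the plan's own threshold. The incomplete follow-up also reaches into the perioperative period: the synopsis defines safe as not interfering with prostatectomy, and section 7.4 records surgical complications as adverse events.

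**Working it through.** **The plan's own figures.** An exact binomial recursion over the printed boundaries (3 of 3 up to 7 of 20, stop when the count reaches the boundary) at a 15% rate gives a stopping probability of 0.0480, against the stated 0.048. Paired t-test power with n = 20, effect size 0.67 and two-sided 0.05 is 0.811, against the stated ≥81%. Both reproduce, and neither depends on when the AE rate is computed.

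**Inputs**
- Men: 20 (section 4.2).
- Entry rate: 2 to 3 per month (section 4.2), taken as evenly spaced. With 30.44 days per month, the gap between men is 15.2, 12.2 or 10.1 days at 2, 2.5 or 3 per month.
- First dose to surgery: 56 days (section 5.4).
- Safety window: 56 + 60 = 116 days after first dose (section 10.1), or 116/30.44 = 3.8 months.

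**Men with open follow-up.** The man who entered k places before the last has been followed for k × gap days. He is open if that is less than the window. The count is therefore window/gap, rounded up.

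| Reading | Window (days) | 2/month | 2.5/month | 3/month |
|---|---|---|---|---|
| Cut at 20th first dose, AEs to postoperative day 60 | 116 | 7.62 → 8 | 9.53 → 10 | 11.43 → 12 |
| Cut at 20th first dose, AEs to 30 days after last dose (section 7): 42 + 30 | 72 | 4.73 → 5 | 5.91 → 6 | 7.10 → 8 |
| Cut at 20th prostatectomy, AEs to postoperative day 60 | 60 | 3.94 → 4 | 4.93 → 5 | 5.91 → 6 |
| Not yet operated on at 20th first dose | 56 | 3.68 → 4 | 4.60 → 5 | 5.52 → 6 |

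The visit tolerances (±3 days for surgery, ±1 week for follow-up) make the first window 106 to 126 days and its count 7 to 13.

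**Effect on the rate.** Expected reported rate = true rate × average share of events already observed across the 20 men. The documents do not say when Grade ≥3 events occur, so the timing below is assumed. The cut is at the 20th first dose and the true rate is 15%.

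| Assumed event timing | Share captured (3/month to 2/month) | 15% would read |
|---|---|---|
| First 14 days after first dose | 0.936 to 0.950 | 14.0% to 14.3% |
| Uniform, first dose to surgery | 0.836 to 0.882 | 12.5% to 13.2% |
| Uniform over 116 days | 0.689 to 0.784 | 10.3% to 11.8% |
| Uniform over the 30 days after surgery | 0.625 to 0.742 | 9.4% to 11.1% |

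The shortfall is thus 15.0 − 14.3 = 0.7 to 15.0 − 9.4 = 5.6 percentage points. With the cut at the 20th prostatectomy and events uniform over 116 days, 91% to 94% are captured, so 15% would read about 14%.

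**In events.** Three of 20 is 15.0% (exact 95% CI 3.2% to 37.9%). If one of the three had not yet occurred at the cut, the report would be 2 of 20, or 10.0% (1.2% to 31.7%).

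**Trial halt.** The men still open are always the most recent 8 to 12 entered, whatever the total. On the day a tenth man is first dosed, 8 to 10 of the 10 would be open.

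**The case against.** The strongest reply is that the sentence is not a data cut. It directly follows the two ways accrual can end and may only name them. The last column of the boundary table supports this: a boundary of 7 at 20 patients means little unless the 20th man has been observed. This reading is possible and cannot be excluded. But the sentence says when the rate is to be calculated, and no other section gives a different time. A plan open to both readings still needs the edit.

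A second reply is that final safety reporting is described elsewhere without this cut. Section 7.5.2 collects adverse events throughout the study, and sections 8.3.1 and 10.4.1 summarise them for all dosed men. The primary endpoint needs the 20th man's prostatectomy tissue, so the complete results cannot be reported at his first dose. This stands in one respect. A reader might infer that the published rate will be biased low, and the documents do not support that: they never say that the figure computed at accrual completion is the one to be published. Those sections cover collection, population and tabulation, however, and do not set a date for this rate and interval.

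A third reply is that 8 to 12 rests on one reading. That is correct. The synopsis definition of evaluable men brings it to 4 to 6, and the 30-day limit in section 7 brings it to 5 to 8. No reading brings it to zero.

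Finally, the size of any bias is assumed, amounts to about one event at most in expectation (20 × 0.056 = 1.1), and is small beside the width of the interval. That is fair as to size. It does not justify a known downward error that waiting removes.

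**Conclusion.** The point holds as a mismatch between the stated calculation time and the stated safety window, with a conditional consequence. Under the literal reading, 8 to 12 of 20 men would be incompletely followed; the other readings give 4 to 8. If the rate were then computed with all dosed men in the denominator, any error from open follow-up would be downward. At a true 15% and a cut at the 20th first dose, the expected figure lies between about 9% and 14%.

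This rests on evenly spaced entry at the planned rate, first dose at entry, surgery at 56 days, and assumed event timing. A reader might settle on 10% to 12% as the figure that would be reported. That range requires substantial risk after surgery, and the documents give no basis for choosing it over the others. Nor do they show that a biased rate will in fact be published.

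**What to change.** In the synopsis, section 10.1 and section 10.5.2, replace the timing sentence with wording such as: *The final proportion of dosed men with at least one Grade ≥3 AE, with its exact 95% CI, will be calculated once every dosed man has completed postoperative day 60 or has left the study. This also applies if the trial halts early.*

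Define completion of accrual once, as the 20th man registered, the 20th dosed or the 20th operated on, and reconcile the sample descriptions in the synopsis and section 4.2. If a figure is wanted earlier, label it interim and give the number of men with open follow-up.

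The cost is the three text changes and the definition. The final rate comes about 3.8 months after the last man's first dose. No visits are added, because the day-60 contact is already scheduled in sections 5.1 and 5.5. The boundary table, the 0.048 and the 81% stay as they are.
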